#### 12.5 REPORTING OF SERIOUS ADVERSE EVENTS AND ADVERSE EVENTS

# 12.5.1 Reporting of Serious Adverse Events to Sponsor

This section describes the responsibilities of the site investigator to report serious adverse events to the Sponsor (DAIT/NIAID) via the eCRF. Timely reporting of adverse events is required by 21 CFR and ICH E6(R2) guidelines.

Site investigators will report all serious adverse events (Section 12.2.3), regardless of relationship or expectedness within 24 hours of discovering the event. Any AESI (Section 12.2.4) or a hypersensitivity/anaphylactic reaction that results in permanent discontinuation of study medication (Section 6.4.1 and Section 12.3.1) will also be reported within 24 hours.

For serious adverse events, all requested information on the AE/SAE eCRF will be provided. However, unavailable details of the event will not delay submission of the known information. As additional details become available, the SAE eCRF should be updated and submitted.

For additional information regarding SAE reporting, contact Rho Product Safety:

#### 12.5.2 Reporting to Health Authority

After an adverse event requiring 24-hour reporting (Section 12.5.1) is submitted by the site investigator and assessed by DAIT/NIAID, there are two options for DAIT/NIAID to report the adverse event to the appropriate health authorities:

# 12.5.2.1 Annual Reporting

DAIT/NIAID will include in the annual study report to health authorities all adverse events classified as:

• Serious, expected, suspected adverse reactions (Section 12.2.1.1)

- Serious and not a suspected adverse reaction (Section 12.2.2)
- Pregnancies.

Note that all adverse events (not just those requiring 24-hour reporting) will be reported in the Annual IND Report.

# 12.5.2.2 Expedited Safety Reporting

This option, with 2 possible categories, applies if the adverse event is classified as one of the following:

Category 1: Serious and unexpected suspected adverse reaction (SUSAR) (see Section 12.2.1.1, Section 12.2.2, and 21 CFR 312.32(c)(1)(i)).

The Sponsor shall report any suspected adverse reaction that is both serious and unexpected. The Sponsor shall report an adverse event as a suspected adverse reaction only if there is evidence to suggest a causal relationship between the study drug and the adverse event, such as:

- 1. A single occurrence of an event that is uncommon and known to be strongly associated with drug exposure (e.g., angioedema, hepatic injury, or Stevens-Johnson Syndrome);
- 2. One or more occurrences of an event that is not commonly associated with drug exposure, but is otherwise uncommon in the population exposed to the drug (e.g., tendon rupture);
- 3. An aggregate analysis of specific events observed in a clinical trial (such as known consequences of the underlying disease or condition under investigation or other events that commonly occur in the study population independent of drug therapy) that indicates those events occur more frequently in the drug treatment group than in a concurrent or historical control group.

# Category 2: Any findings from studies that suggests a significant human risk

The Sponsor shall report any findings from other epidemiological studies, analyses of adverse events within the current study or pooled analysis across clinical studies or animal or *in vitro* testing (e.g. mutagenicity, teratogenicity, carcinogenicity) that suggest a significant risk in humans exposed to the drug that would result in a safety-related change in the protocol, informed consent, current IB or other aspects of the overall conduct of the study.

DAIT/NIAID shall notify the FDA and all participating investigators of expedited Safety Report within 15 calendar days; unexpected fatal or immediately life-threatening suspected adverse reaction(s) shall be reported as soon as possible or within 7 calendar days.

#### 12.5.3 Reporting of Adverse Events to IRB/IECs

All investigators shall report adverse events, including expedited reports, in a timely fashion to their respective IRBs/IECs in accordance with applicable regulations and guidelines. All Safety Reports to the FDA shall be distributed by DAIT/NIAID or designee to all participating institutions for site IRB/IEC submission.

#### 12.6 PREGNANCY REPORTING

The investigator shall be informed immediately if a female study participant becomes pregnant, or if a male participant becomes aware of a pregnancy in a female partner. A pregnant participant shall be instructed to stop taking study medication. The investigator shall counsel the participant, and discuss the risks of continuing with the pregnancy and the possible effects on the fetus. Monitoring of a pregnant participant shall continue until the conclusion of the pregnancy.

The investigator shall report to DAIT/NIAID all pregnancies that occur in female study participants within 1 business day of becoming aware of the event using the Pregnancy eCRF. All female participant pregnancies identified during the study shall be followed to conclusion and the outcome of each must be reported. The Pregnancy eCRF shall be updated and submitted to the CDSMC when details about the outcome are available.

Information requested about the delivery shall include:

- Gestational age at delivery
- Birth weight, length, and head circumference
- Gender
- Appearance, pulse, grimace, activity, and respiration (APGAR) score at 1 minute, 5 minutes, and 24 hours after birth, if available
- Any abnormalities.

For all pregnancy complications that result in a congenital abnormality, birth defect, miscarriage, and medically indicated abortion, an SAE shall be submitted to DAIT/NIAID using the SAE reporting procedures described above.

The investigator shall also report to DAIT/NIAID all male participant partner pregnancy outcomes by eCRF when this information can be obtained. Specific information collected will include number of infants; gender, weight, length, and head circumference of each infant; any infant complications, medical problems, or congenital anomalies.

# 12.7 REPORTING OF OTHER SAFETY INFORMATION

An investigator shall promptly notify the site IRB as well as DAIT/NIAID when an "unanticipated problem involving risks to participants or others" is identified, which is not otherwise reportable as an adverse event.

#### 12.8 REVIEW OF SAFETY INFORMATION

#### 12.8.1 Medical Monitor Review

The DAIT/NIAID Medical Monitor shall receive monthly reports from the SCCC compiling new and accumulating information on AEs, SAEs, and pregnancies recorded by the study site(s) on appropriate eCRFs.

In addition, the Medical Monitor shall review and make decisions on the disposition of the SAE (Section 12.5.1) and pregnancy reports (Section 12.6) received by the CDSMC.

#### 12.8.2 DSMB Review

#### 12.8.2.1 Planned DSMB Reviews

The NIAID Autoimmune DSMB will review safety data and make recommendations regarding the continuation, termination, or modification of the study. The DSMB shall review safety data at least yearly during planned DSMB Meetings. Data for the planned safety reviews will include, at a minimum, a listing of all reported AEs and SAEs. The DSMB will also review F-VASI and T-VASI results through Week 12 by treatment group in a closed session to monitor for an unexpected drug-induced worsening of vitiligo.

The DSMB will be informed of an Expedited Safety Report in a timely manner.

#### 12.8.2.2 Ad hoc DSMB Reviews

In addition to the pre-scheduled data reviews and planned safety monitoring, the DSMB may be called upon for *ad hoc* reviews. The DSMB will review any event that potentially impacts safety at the request of the protocol chair or DAIT/NIAID. In addition, the following events will trigger an *ad hoc* comprehensive DSMB Safety Review:

- Any death that occurs in the study, which is possibly related or related to study medication (Table 4).
- The occurrence of a Grade 3 or higher SAE related to study treatment that is also a SUSAR in one or more of the study participants who have received study treatment.
- Any occurrence of a Grade 3 or higher anaphylaxis reaction (Table 3).
- Two or more events of skin malignancy in individuals who receive nbUVB during the study.

The DSMB will review the data within 2 weeks of the event being identified. If the DSMB has not reviewed the data within 2 weeks, study enrollment, as defined in Section 8.1, will be suspended and no additional participants will sign consent. Participants already in screening may continue with screening assessments, and participants already enrolled in the trial will continue as planned, pending completion of the DSMB *ad hoc* review. After review of the data, the DSMB will make recommendations regarding study conduct and/or continuation.

#### 13. STATISTICAL CONSIDERATIONS AND ANALYTICAL PLAN

#### 13.1 OVERVIEW

ITN086AI is a Phase 2a, randomized, double-blind, placebo controlled trial in which participants with vitiligo will receive AMG 714 or placebo. The primary objective is to determine the efficacy of IL-15 inhibition with AMG 714 at inducing facial skin repigmentation compared to placebo. The study also aims to evaluate safety and assess the durability of repigmentation with AMG 714.

# 13.2 ENDPOINTS

Primary and secondary endpoints are listed in Sections 3.2 and 3.3.

#### 13.3 MEASURES TO MINIMIZE BIAS

This study has a randomized, double-blind, placebo-controlled, prospective design with well-defined entry criteria. Participants and site personnel who manage participants will be blinded to treatment assignment throughout the trial. In addition, site personnel, including investigators, will not have access to any mechanistic data until completion of the study.

#### 13.4 ANALYSIS PLAN

#### 13.4.1 Analysis Populations

**Safety sample (SS):** All participants who receive any amount of AMG 714 or placebo. The safety analyses will be based on the actual treatment the participants receive.

**Modified Intent to treat (mITT) sample:** All randomized participants who receive any dose of study treatment. The efficacy analyses will be based on the mITT sample according to the group to which the participants are assigned.

**Per protocol (PP) sample:** All participants in the mITT sample with no major protocol deviations that impact efficacy assessments, who received at least 5 of the 6 doses of the expected study treatment, and who have the Week 24 F-VASI assessment. The reported major deviations will be reviewed during a masked data review after the last participant's primary endpoint visit to determine which participants should be excluded from the per-protocol population.

# 13.4.2 Primary Analysis of Primary Endpoint

The primary endpoint is the proportion of participants achieving an F-VASI35 response at Week 24.

The primary analysis of the primary endpoint will be performed on the mITT sample and is designed to test the following hypotheses:

- Null hypothesis: The proportion achieving an F-VASI35 at Week 24 does not differ between the AMG 714 and placebo groups
- Alternate hypothesis: The proportion achieving an F-VASI35 at Week 24 differs between the AMG 714 and placebo groups.

The proportion of F-VASI35 responders will be estimated for each treatment group. Groups will be compared using two-sided Fisher's Exact test evaluated using a Type 1 error rate of  $\alpha$ =0.05.

**Missing Data.** For a participant who is missing the baseline F-VASI, the screening F-VASI will be used. Participants for whom the Week 24 F-VASI cannot be evaluated will be deemed non-responders.

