## 13.4.4 Analyses of Secondary Endpoints

All secondary inferential analyses are considered supportive; p-values for test of differences among groups will be presented without adjustment for multiple comparisons. The mITT population will be used for all secondary analyses. For secondary response indices (e.g. F-VASI25 at Week 12, F-VASI25 at Week 36, F-VASI25 at Week 48, T-VASI25 at Week 12, etc.), participants for whom endpoint data is unavailable will be deemed response failures. Otherwise, data will not be imputed for analyses of secondary endpoints.

The null hypothesis proposes that there are no differences in the secondary endpoints (measured either as means or proportions) between study groups. The alternative hypothesis proposes that there are differences between groups.

The following analyses are planned to evaluate the impact of treatment over the course of the study:

- 1. For secondary dichotomous response variables including F-VASI25, F-VASI35, F-VASI35, F-VASI50, F-VASI75, F-VASI90, T-VASI25, T-VASI35, T-VASI50, T-VASI75, and T-VASI90 at each indicated secondary analysis time point, analyses will be analogous to those described for the primary endpoint.
- 2. Estimated response rates for each dichotomous F-VASI and T-VASI responder variable (i.e. 25%, 35%, 50%, 75%, 90%) at each indicated analysis time point will be presented for subgroups defined by treatment and active/stable vitiligo status.
- 3. For the change (and % change) in F-VASI, change (and % change) in T-VASI, change in VES, and change in VitiQoL at each indicated secondary analysis time point, the treatment group distributions will be compared using Mann-Whitney tests (2-sided).
- 4. For the ordinal VNS endpoint at each secondary analysis time point,
  - a. Treatment groups will be compared at each indicated secondary analysis time point using an extension of the Fisher's Exact test.
  - b. Shifts in distributions from baseline to each time point will be evaluated for each treatment arm using Bowker's exact test of symmetry.

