#### 13.7 SAMPLE SIZE CONSIDERATIONS

The underlying F-VASI35 response rate at Week 24 was assumed to be 5% for the placebo arm based on clinical trial results with ruxolitinib cream for vitiligo. For the AMG 714 arm, the minimal clinically meaningful response rate was assumed to be 45%. Under this scenario, a study of 57 individuals randomized 2:1 to AMG 714 and placebo, respectively, will provide 88% power using a 2-sided Fisher's Exact test at  $\alpha$ =0.05. If the placebo response rate is actually 7.5% (i.e. 50% higher than expected), power will still 81%. For the secondary PP analysis, if sample size drops to 48 (16% loss), then power is still 80%.

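### Optional improvement: at 38 v 19, Boschloo's exact test would replace the valid but conservative Fisher test and add about 2 to 3.5 points of primary power, with type I error still at or below 5%

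*Combined protocol and SAP*

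**What the plan says.** Section 13.4.2 sets the primary analysis on the mITT sample: "Groups will be compared using two-sided Fisher's Exact test", at a type I error rate of 0.05. A participant whose Week 24 F-VASI cannot be evaluated counts as a non-responder, so missing data do not shrink the arms.

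Section 13.7 powers the trial on the same test. The "F-VASI35 response rate at Week 24 was assumed to be 5% for the placebo arm". For AMG 714 it takes 45% as the minimal clinically meaningful rate. It concludes that "a study of 57 individuals randomized 2:1 to AMG 714 and placebo" "will provide 88% power using a 2-sided Fisher's Exact test". It also gives 81% power if the placebo rate is 7.5%, and 80% for the per-protocol (PP) analysis if the sample falls to 48.

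The choice of test carries further. Section 13.4.3 repeats it for the observed-data and PP sensitivity analyses. Section 13.4.4 item 1 says of the secondary responder variables that "analyses will be analogous to those described for the primary endpoint". The documents do not discuss how conservative Fisher's test is at these arm sizes, and they mention no unconditional exact test.

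**The concern.** Fisher's test conditions on the total number of responders. This design fixes the two arm sizes but not that total. In small samples the conditional distribution is coarse, so the rejection region usually falls well short of the nominal 5%. An unconditional exact test can enlarge the region and still hold type I error at or below 5% whatever the common response rate is.

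At stake is a modest amount of power in a 57-person proof-of-concept trial with only 19 placebo participants. Section 1.4.2 states that AMG 714 has not been studied in vitiligo, so the 45% rate has no direct clinical support, and some protection against a higher placebo rate or a smaller effect is worth having if it costs almost nothing.

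**Working it through.** **Inputs.** From Section 13.7: N = 57 at 2:1, hence 38 AMG 714 and 19 placebo; rates 45% v 5% and 45% v 7.5%; two-sided alpha 0.05; PP N = 48. The split of the 48 is not given, and 32 v 16 is assumed.

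**1. Reproduce the plan's power.** The arcsine approximation with continuity correction is

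Φ( 2√(n₁n₂/N) · [asin√(p₁ − 1/(2n₁)) − asin√(p₂ + 1/(2n₂))] − 1.96 ),

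with 1 = AMG 714 and 2 = placebo.

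- 45% v 5%, N = 57: 2√(38·19/57) = 7.118. The arcsine terms are 0.7221 and 0.2799. Then 7.118 × 0.4422 = 3.147, and Φ(3.147 − 1.96) = 88.2% (stated 88%).
- 45% v 7.5%, N = 57: the placebo term becomes 0.3239, giving 80.9% (stated 81%).
- 45% v 5%, N = 48: 2√(32·16/48) = 6.532. The terms are 0.7196 and 0.2891, giving 80.3% (stated 80%).

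All three stated figures match this approximation.

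**2. Exact power and size of Fisher's test.** Enumerate all 39 × 20 tables (x, y). Add Bin(x; 38, p₁) · Bin(y; 19, p₂) over those with two-sided Fisher p ≤ 0.05.

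- Power: 92.7% (45% v 5%), 85.8% (45% v 7.5%) and 85.7% (45% v 5%, 32 v 16).
- Size at a common rate of 5%, 10%, 20% and 30%: 1.4%, 2.7%, 3.6% and 3.6%. The maximum over all rates is 3.8% (3.2% at 32 v 16).

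**3. Boschloo's test.** For an observed table, p_B = max over π of Pr_π{Fisher p of (X, Y) ≤ observed Fisher p}, where both arms respond at rate π. Reject if p_B ≤ 0.05. At 38 v 19 this is the same as rejecting when the Fisher p is at most 0.068. The maximum size is then 4.94%. Admitting the next table in the ordering (16/38 v 3/19, Fisher p = 0.073) would raise it to 5.2%. The region contains every table that Fisher rejects. At 32 v 16 the maximum size is 4.7%.

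**4. Power compared.**

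| Scenario | Fisher (exact) | Boschloo | Gain (points) |
|---|---|---|---|
| 38 v 19, 45% v 5% (protocol) | 92.7% | 95.1% | 2.4 |
| 38 v 19, 45% v 7.5% (protocol) | 85.8% | 89.3% | 3.5 |
| 32 v 16, 45% v 5% (PP, split assumed) | 85.7% | 90.1% | 4.3 |
| 38 v 19, 40% v 5% (assumed) | 85.6% | 89.6% | 4.0 |
| 38 v 19, 35% v 5% (assumed) | 75.1% | 79.8% | 4.7 |
| 38 v 19, 40% v 7.5% (assumed) | 75.1% | 80.9% | 5.8 |
| 38 v 19, 35% v 7.5% (assumed) | 61.7% | 68.5% | 6.8 |

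Gains are taken from unrounded powers.

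**5. Where the gain comes from.** At the design rates nearly all of it is two tables, 13/38 v 2/19 and 14/38 v 2/19. The probability of 2/19 at 5% is 0.179, and those of 13/38 and 14/38 at 45% are 0.054 and 0.079. So 0.179 × 0.133 = 0.024, which is the 2.4 points. Under the null, the size at a common 5% rate is 1.4% for both tests. At 20% it rises from 3.6% to 4.7%. The added rejections lie in tables with more responders than a 5% null rate produces.

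**6. The two-sided convention matters.** The alternative is to double a one-sided Boschloo p-value.

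| Table | Fisher p | Boschloo, two-sided order | Boschloo, doubled one-sided |
|---|---|---|---|
| 13/38 v 2/19 | 0.065 | 0.049 | 0.058 |
| 14/38 v 2/19 | 0.059 | 0.048 | 0.038 |
| 16/38 v 3/19 | 0.073 | 0.052 | 0.049 |

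The two versions disagree at 0.05 on the first and third tables. The doubled version gives 94.8% and 89.3% power in the two protocol scenarios at N = 57, and 88.2% at 32 v 16.

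**The case against.** The strongest reply is that nothing needs repair. Fisher's test is prespecified, it agrees between Sections 13.4.2 and 13.7, and its exact power exceeds the stated power in every scenario that the plan names. Conditioning on total responders is a respectable choice, and it needs neither a search over an unknown rate nor a choice of two-sided convention. All of this stands, and it is why the point is an optional improvement. It is not a reason against a test that contains Fisher's rejection region and still holds type I error at or below 5%.

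Three stronger readings are tempting, and none is supported.

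- A reader might set 95.1% against the stated 88% and infer a gain of about 7 points. Section 13.7's figure is an approximation; from 88% to 92.7% is approximation error, and only the last 2.4 points belong to Boschloo.
- A reader might infer that Boschloo recovers the error left unused at the assumed 5% placebo rate. Its size there is also 1.4%.
- A reader might quote gains of 4 to 7 points as primary power. At N = 57 those need an AMG 714 rate of 35 to 40%, below the 45% that Section 13.7 calls minimally meaningful. The 4.3 points at 32 v 16 belong to a sensitivity analysis.

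The secondary endpoints are a weaker argument for change. Section 13.4.4 calls those analyses supportive and leaves them unadjusted. A less conservative test across 39 comparisons (3 for F-VASI35, 4 × 4 for the other F-VASI thresholds, 5 × 4 for T-VASI) would yield more nominally significant results, some of them false, although each test stays at or below 5%.

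**Conclusion.** The point holds as a cheap efficiency gain. Replacing Fisher by Boschloo, ordered by the two-sided Fisher p-value, adds 2.4 points of primary power at 45% v 5% and 3.5 points at 45% v 7.5%. It cannot lose power, and its maximum type I error is 4.94%. These figures assume realised arms of exactly 38 and 19; the PP figure also assumes 32 v 16. With other arm sizes the numbers shift, but the containment of Fisher's region and the 5% bound remain. Keeping Fisher's test would also be acceptable.

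**What to change.** Before unblinding, name in Section 13.4.2 Boschloo's unconditional exact test as the primary test: ordered by the two-sided Fisher p-value, maximised over the common response rate, two-sided alpha 0.05, computed on the realised arm sizes. Report the Fisher p-value as a sensitivity analysis. The observed-data and PP analyses in Section 13.4.3 would follow, since they are defined by analogy to the primary analysis.

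Restate Section 13.7 by exact enumeration for the chosen test: 95.1%, 89.3% and, with the split stated, 90.1%. If Fisher is kept, the exact figures are 92.7%, 85.8% and 85.7%.

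Extending the test to the secondary responder endpoints is optional. Section 13.4.4 item 1 should say which test applies, because its present wording would carry any change over automatically.

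The cost is SAP wording and a short validated program, with no change to participants, visits, endpoint, alpha or missing-data rule. Readers know the test less well than Fisher's. The software must also be checked: at least one common routine (boschloo_exact in scipy) returns the doubled one-sided version, which would reverse the conclusion for some tables.

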#### 13.4.3 Supportive Analyses of the Primary Endpoint(s)/Outcome(s)

At a minimum, the following sensitivity analyses for the primary analyses will be performed:

- An analysis analogous to the primary endpoint analysis using only mITT participants with observed F-VASI data at Week 24 (i.e., dropping participants with missing Week 24 F-VASI rather than assuming non-response)
- An analysis analogous to the primary endpoint analysis using the PP participants
- A stratified analysis of F-VASI35 response using the Cochran-Mantel-Haenszel statistic to compare treatment groups after controlling for active versus stable vitiligo at baseline.

## 13.4.4 Analyses of Secondary Endpoints

All secondary inferential analyses are considered supportive; p-values for test of differences among groups will be presented without adjustment for multiple comparisons. The mITT population will be used for all secondary analyses. For secondary response indices (e.g. F-VASI25 at Week 12, F-VASI25 at Week 36, F-VASI25 at Week 48, T-VASI25 at Week 12, etc.), participants for whom endpoint data is unavailable will be deemed response failures. Otherwise, data will not be imputed for analyses of secondary endpoints.

The null hypothesis proposes that there are no differences in the secondary endpoints (measured either as means or proportions) between study groups. The alternative hypothesis proposes that there are differences between groups.

The following analyses are planned to evaluate the impact of treatment over the course of the study:

- 1. For secondary dichotomous response variables including F-VASI25, F-VASI35, F-VASI35, F-VASI50, F-VASI75, F-VASI90, T-VASI25, T-VASI35, T-VASI50, T-VASI75, and T-VASI90 at each indicated secondary analysis time point, analyses will be analogous to those described for the primary endpoint.
- 2. Estimated response rates for each dichotomous F-VASI and T-VASI responder variable (i.e. 25%, 35%, 50%, 75%, 90%) at each indicated analysis time point will be presented for subgroups defined by treatment and active/stable vitiligo status.
- 3. For the change (and % change) in F-VASI, change (and % change) in T-VASI, change in VES, and change in VitiQoL at each indicated secondary analysis time point, the treatment group distributions will be compared using Mann-Whitney tests (2-sided).
- 4. For the ordinal VNS endpoint at each secondary analysis time point,
  - a. Treatment groups will be compared at each indicated secondary analysis time point using an extension of the Fisher's Exact test.
  - b. Shifts in distributions from baseline to each time point will be evaluated for each treatment arm using Bowker's exact test of symmetry.

5. To evaluate treatment group differences longitudinally, separate general mixed linear models will be fit to the F-VASI, T-VASI, VES, and VitiQoL, over all time points from day 0 through Week 24 with fixed effects for time point (fit as categorical), treatment group and the time\*treatment interaction. A 1-banded unstructured within-subject covariance matrix will be assumed and fit separately for each treatment arm. Appropriate contrasts will evaluate trends over time and changes from baseline.

After Week 24, participants who do not achieve a T-VASI25 response will receive nbUVB phototherapy. For T-VASI25 responders (who will not receive nbUVB phototherapy), the post-Week 24 analyses will evaluate durability of response. In contrast, for T-VASI25 non-responders, the aim will be to evaluate improvement following the addition of nbUVB phototherapy. The following analyses are planned:

- 1. Durability of response: For the subset of participants who achieve a T-VASI25 response at Week 24 (and receive no nbUVB phototherapy), the null hypothesis of no change from Week 24 to Week 48 will be evaluated by treatment arm against the 1-sided alternative of worsening from Week 24 to Week 48.
  - a. For each treatment arm, descriptive statistics and p-values derived from Wilcoxon tests will be presented for change (and % change) in F-VASI, change (and % change) in T-VASI, change in VES, and change in VitiQoL from Week 24 to Week 48.
  - b. For the VNS ordinal endpoint, shifts in distributions from Week 24 to Week 48 will be evaluated for each treatment arm using Bowker's exact test of symmetry.
- 2. Improvement after nbUVB phototherapy: For the subset of participants who do not achieve a T-VASI25 response at Week 24 and receive nbUVB phototherapy, analyses will assess improvement in repigmentation and other key scales in the AMG 714 and placebo arms following nbUVB phototherapy.
  - a. For each treatment arm, descriptive statistics and p-values derived from Wilcoxon tests will be presented for change (and % change) in F-VASI, change (and % change) in T-VASI, change in VES, and change in VitiQoL from baseline to Week 48.
  - b. For dichotomous response indices defined by % improvement from baseline to Week 48 (i.e. F-VASI25, F-VASI35, F-VASI50, F-VASI75, F-VASI90, T-VASI25, T-VASI35, T-VASI50, T-VASI75, and T-VASI90), estimated response rates will be presented for subgroups defined by treatment.
  - c. For the VNS ordinal endpoint at Week 48,
    - i. Shifts in distributions from baseline to Week 48 will be evaluated for each treatment arm using Bowker's exact test of symmetry.

Treatment group differences for the incidence of AEs and the incidence of grade 3 or higher infectious AEs occurring over the first 24 weeks will be compared using a Fisher's exact test.

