### 2.3 SECONDARY OBJECTIVES

The secondary objectives are to:

- 1. Evaluate the safety and tolerability of AMG 714 in vitiligo.
- 2. Determine the efficacy of IL-15 inhibition with AMG 714 at inducing total body skin repigmentation in vitiligo.
- 3. Assess the durability of the skin repigmentation achieved by AMG 714 in vitiligo.
- 4. Evaluate the efficacy of AMG 714 followed by narrow band UVB (nbUVB) phototherapy.

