#### 7.3 NARROW BAND UVB PHOTOTHERAPY

Light or laser-based treatments (phototherapy) are prohibited for all study participants except as described below:

Participants will undergo narrow band ultraviolet B (nbUVB) phototherapy if T-VASI does not improve by  $\geq 25\%$  at Week 24 compared to Week 0. Phototherapy will be administered in

accordance with the Vitiligo Working Group expert recommendations. Narrow band UVB phototherapy must be started within 28 days of the Week 24 study visit.

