#### 11.4 FOLLOW-UP AFTER STUDY WITHDRAWAL

If a participant withdraws or is withdrawn from the study as described in Section 11.2, the participant will be asked to return for a final visit where the assessments outlined in the withdrawal (WD) visit in Appendix 1 will be performed. No additional follow-up will be requested from participants after early study withdrawal.

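### The durability analysis leaves out any Week 24 T-VASI25 responder without a Week 48 score; if responders who lose pigment leave more often, durability could be overstated, so two supportive analyses are worth adding.

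*Combined protocol and SAP*

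**What the plan says.** Section 2.3 lists as a secondary objective: "Assess the durability of the skin repigmentation achieved by AMG 714 in vitiligo". The dedicated analysis is durability item 1 in Section 13.4.4. Its set and hypothesis read: "For the subset of participants who achieve a T-VASI25 response at Week 24 (and receive no nbUVB phototherapy), the null hypothesis of no change". Each arm is tested separately, "against the 1-sided alternative of worsening from Week 24 to Week 48". The method is: "descriptive statistics and p-values derived from Wilcoxon tests will be presented for change (and % change) in F-VASI". T-VASI, VES and VitiQoL are treated in the same way, and the noticeability scale has Bowker's test.

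The general rule for secondary endpoints, earlier in Section 13.4.4, counts missing data as failure for response indices. It then adds: "Otherwise, data will not be imputed for analyses of secondary endpoints". A change score from Week 24 to Week 48 is not a response index, so a responder without a Week 48 value contributes nothing to item 1.

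The Schedule of Events (Appendix 1) marks F-VASI and T-VASI at Weeks 24, 36 and 48, at the withdrawal visit and at unscheduled visits. Section 11.4 asks participants who withdraw to attend that withdrawal visit. Item 1 uses only Weeks 24 and 48.

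**The concern.** Phototherapy is decided once, from the Week 24 T-VASI. A responder who loses pigment afterwards falls under this general rule in Section 7.3: "Light or laser-based treatments (phototherapy) are prohibited for all study participants except as described below". Section 7.2 bars most immunomodulators, and Section 7.5 provides no rescue medication. Such a person could have a motive to leave that a stable responder lacks. If so, the missing Week 48 scores would tend to be the bad ones.

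The direction of the test adds to this. The alternative is worsening, so a non-significant result is likely to be read as maintained response. Losing relapsers reduces both the estimated worsening and the power to see it. Both effects lean towards durability, which is a stated objective and part of the clinical hypothesis in Section 2.1.

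**Working it through.** **Plan's own figure.** There is none for durability. The power statement in Section 13.7 (88% for 57 participants, 45% against 5%) concerns the Week 24 F-VASI35 comparison. It reproduces at 88.3% with an arcsine approximation with continuity correction and has no bearing here. It gives only a rough scale for the subset: 45% of 38 is 17.1 responders on AMG 714, if the F-VASI35 assumption is borrowed for T-VASI25.

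**Illustration 1 (assumed inputs).** There are 15 responders in the AMG 714 arm. Six relapse by 25 points on the percentage scale, nine do not change, and the SD is 10. The test is a one-sided Wilcoxon signed-rank test at 0.05, simulated. If d relapsers leave and are dropped:

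- relapse share = (6 − d)/(15 − d)
- expected mean worsening = 25 × (6 − d)/(15 − d)

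| d | Relapse share | Mean worsening | Detection |
|---|---|---|---|
| 0 | 6/15 = 40% | 150/15 = 10.0 | about 71% |
| 2 | 4/13 = 31% | 100/13 = 7.7 | about 41% |
| 3 | 3/12 = 25% | 75/12 = 6.25 | about 26% |
| 4 | 2/11 = 18% | 50/11 = 4.5 | about 14% |

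Repeat simulations moved these detection rates by only a point or two.

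**Illustration 2 (other assumed inputs).** Relapse means 30 points lost, SD 10.

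| Responders | Relapse | Relapsers who leave | Mean worsening, all → observed | Detection, all → observed |
|---|---|---|---|---|
| 17 | 30% | a quarter | 9.0 → 7.3 | 56% → 40% |
| 17 | 30% | half | 9.0 → 5.4 | 56% → 25% |
| 17 | 50% | half | 15.0 → 10.0 | 91% → 50% |
| 9 | 30% | half | about 9 → 5.4 | about 33% → 14% |

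**If leaving is unrelated to relapse.** Take Illustration 1 with 2 of 6 relapsers and 3 of 9 others leaving. The mean is 25 × 4/10 = 10.0, unchanged. Power still falls, because 10 people remain instead of 15.

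**What the alternatives do in Illustration 1.**

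- *Maintained share over all responders, missing counted as not maintained* (taking each relapser to be below T-VASI25 at Week 48): 9/15 = 60%, whichever relapsers leave. Among completers it would be 9/13 = 69%, 9/12 = 75% or 9/11 = 82%.
- *Withdrawal score used, assumed to show 15 of the 25 points lost:* means (100 + 30)/15 = 8.7, (75 + 45)/15 = 8.0 and (50 + 60)/15 = 7.3 for d = 2, 3 and 4. Detection is about 65%, 62% and 58%, against 41%, 26% and 14% when these people are dropped.
- *Worst rank for leavers, no true relapse at all:* false rejection rises from about 5% to about 9% with one unrelated leaver among 15, about 16% with two and 41% with four.
- *Carrying forward a score taken before the relapse* (no change recorded): means 100/15 = 6.7 and 75/15 = 5.0 for d = 2 and 3. Detection is 35% to 38% (d = 2) and 23% (d = 3), slightly worse than dropping.

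**The case against.** The case for leaving the plan alone has substance. A reader might infer that relapse itself removes the data. The documents do not show this. Section 11.2 does not require a relapser to leave. Section 8.4 adds remote contact between visits after Week 12, Section 8.6 offers unscheduled visits when disease activity increases, and Section 11.4 asks for a withdrawal visit. Nor are leaving or breaking the protocol the only routes to treatment: Section 7.1.2 permits limited courses of systemic and topical corticosteroid.

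A reader might also infer that a relapser who starts another treatment will look maintained. For phototherapy, the wording of item 1 restricts the set to people who receive none, so that person appears to leave the set. For other prohibited agents, the reading assumes protocol breaches at an unknown rate. What stands is narrower: no analysis rule covers scores taken after such treatment.

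A third inference, that durability *is* overstated, goes too far. The subset is selected on a Week 24 threshold, so regression to the mean pushes towards apparent worsening. The net direction is not settled.

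The F-VASI and T-VASI response indices at Weeks 36 and 48 do count missing as failure. They cover the whole mITT sample, including Week 24 non-responders and phototherapy recipients, and so do not isolate maintenance. Finally, Section 13.4.4 calls all secondary inference supportive, and this is a within-arm test with no stated power in a Phase 2a trial. That limits the stakes.

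**Conclusion.** The point holds as a conditional one. Item 1 excludes every Week 24 T-VASI25 responder without a Week 48 score, and no other planned analysis measures maintenance among all of those responders. If people who lose pigment leave more often, durability could be overstated and the one-sided test would lose power in the direction that favours durability. In the illustrations where half of the relapsers leave, detection falls by roughly half, from 56% to 25% or from 91% to 50%. Where leaving is unrelated to relapse, the mean is not biased.

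The number of responders, the relapse rate, the size of relapse, the SD, the test level and the dropout pattern are all assumptions, so the size cannot be fixed from the documents. This is a low-cost improvement to a supportive analysis. It does not affect the primary result.

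**What to change.** Keep the planned observed-case Wilcoxon analysis and add two supportive analyses to durability item 1.

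(a) By arm, give the proportion of all Week 24 T-VASI25 responders who still meet T-VASI25 against Week 0 at Week 48. Count as not maintained a missing Week 48 score, or the start after Week 24 of a vitiligo treatment prohibited by Section 7.2 or of phototherapy outside Section 7.3. Courses permitted by Section 7.1.2 do not count. This follows the plan's own rule for response indices.

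(b) Repeat the F-VASI and T-VASI change analysis with the withdrawal-visit score in place of a missing Week 48 score, where one was taken.

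Report by arm how many responders lack a Week 48 score, and why. Do not make worst rank or an earlier carried-forward score the main analysis.

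The cost is some wording, one derivation and one table, from data already scheduled. There are two downsides. In (a), a participant who leaves for an unrelated reason counts as not maintained: in Illustration 1, two such leavers among the nine stable responders would turn 9/15 = 60% into 7/15 = 47%. In (b), follow-up is shorter than 24 weeks for those who leave, and people who skip the withdrawal visit stay missing. The observed-case result beside both lets the reader judge.
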